4.1 Inclusion criteria

- (1) Age ≥ 18 years old
- (2) According to the updated NF 1 diagnostic criteria of the National Institutes of Health (NIH) in 2021,
 - ① 6 or more CALMs: $d > 5$ mm before puberty or $d > 15$ mm after puberty;

② 2 or more neurofibromas of any type or 1 plexiform neurofibroma;

③ Plaques in the axillary or inguinal area;

④ Optic glioma (OPG);

⑤ Slit lamp examination of two or more Lisch nodules, or optical coherence tomography (OCT) / imaging of two or more near infrared (NIR) choroid abnormalities;

⑥ Characteristic bone lesions, such as sphenoid dysplasia and anterolateral curvature of the tibia;

⑦ Pathogenic heterozygous NF 1 variants with allelic variant scores of 50% in normal tissues (such as leukocytes);

Patients with no parental history and fulfilling 2 or more clinical characteristics could be diagnosed with NF 1

Parents with a history of 1 or more clinical features can be diagnosed with NF 1

(3) Before enrollment, a head and neck surgeon performed a pathological biopsy of the solid tumor to clarify the pathological diagnosis and exclude the malignant peripheral schwannoma (MPNST)

(4) At least one measurable tumor lesion according to the efficacy evaluation criteria of solid tumors RECIST 1.1

(5) The tumor did not invade the brain, spine and other important organs, and there are indications for surgical resection and surgical treatment

(6) The performance status of the Eastern Cooperative Oncology Group (Eastern Cooperative Oncology Group, ECOG) was 0-1

(7) Blood routine: white blood cell count (WBC) 3.010^9 / L; Absolute neutrophil count (ANC) 1.510^9 / L; Platelet (PLT) 10010^9 / L; hemoglobin level (HGB) 9.0 g/dL (no corresponding supportive care, such as transfusion and increased leukocytes within 7 days).

(8) Liver function: 2.5 times aspartate aminotransferase (AST) and alanine aminotransferase (ALT); albumin (ALB) 30 g / L.

(9) Renal function: serum creatinine 1.5 times ULN or creatinine clearance (CrCl) 50 mL/min (using the Cockcroft / Galt formula); urinary protein (UPRO) <(+ +), or 24-hour urinary protein <1.0 g.

(10) Cardiac function: blood creatine phosphokinase 200U / L, left ventricular ejection fraction (LVEF) 50%;

(11) Did not participate in other clinical trials within the previous 30 days;

(12) Patients who voluntarily participate in the project and sign the informed consent form.

4.2 Exclusion criteria

(1) The patient had abnormal blood indexes, abnormal liver and kidney heart function, and cannot tolerate the clinical study process after multidisciplinary consultation and evaluation

(2) The patient has become malignant peripheral nerve schwannoma (MPNST) or has serious complications such as other malignant tumors and heart disease, or has been treated with anti-tumor therapy such as chemotherapy and radiotherapy

(3) The whole clinical study cannot be completed due to personal, social and economic reasons

(4) There are previously serious systemic system diseases and the disease cannot be cured or drug control

(5) Patients who are present in pregnancy

4.3 Lifestyle considerations (lifestyle related restrictions: smoking, drinking, exercise, diet, etc., and what measures will be taken if the subject needs drugs, treatments or surgery prohibited in the protocol)

After entering the clinical study, the subject needs a light diet, food, tobacco, alcohol, and no strenuous exercise. If the subject needs

the drug, treatment or surgery unrelated to the study, the investigator needs to evaluate whether the cause of the need for the drug, treatment and surgical treatment is the adverse event of the study, additional treatment due to accident or other reasons, consider the impact of the treatment on the course of the study, then advise the subject to receive conventional treatment after withdrawal and seal the subject data.

4.4 Screening failures (definition of screening failures and how to process screening failed subjects)

Screening failure refers to the recruitment of subjects who failed to meet the inclusion criteria or the exclusion criteria after multidisciplinary evaluation. The study will inform the results of the multidisciplinary consultation and give the current best treatment advice.

4.5 Recruitment and retention strategy (how to recruit subjects (location, method, expected number.....); How to retain subjects (multiple contact information, incentive); such as involving vulnerable groups: reason + safeguard measures; if having compensation or incentive measures: object, quantity, form, time, etc.)

This study will take offline, combining online recruiting subjects, offline main location for sun Yat-sen memorial hospital oral and maxillofacial surgery, including but not limited to posters, leaflets, lectures and other forms to attract more subjects, each interested patients on-site registration, leave contact information and continue to one-on-one explanation. If the subject is in financial difficulties, the investigator team will assist the subject in providing assistance with the charity fund application to reduce the financial burden of the subject.

5. research design

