2. 1 Research theoretical basis / background (explain why clinical studies are conducted from the limitations of disease, standard of treatment and known treatment, and explain the findings and importance of preclinical, pharmacological and related studies)

Neurofibromatosis (NF) has been included in the list of rare diseases in many countries including China, 96% of which are NF 1 subtypes, and

the clinical manifestations of NF 1 are diverse^[1], involving multiple systems and can cause serious complications such as airway obstruction, spinal cord compression and motor dysfunction^[2-4]. Plexiform neurofibromas (PN) occur in 30 to 50% of NF 1 patients^[5, 6], PN progress fast, accompanied by serious appearance defects, high disability, and the risk of deterioration^[7-10]. According to the 2023 edition of the multidisciplinary diagnosis and treatment of type I neurofibromatosis, patients with NF 1 are more likely to have a variety of benign and malignant tumors than the normal population, including pNF, CNF, MPNST and OPG. Attention should be paid to the early identification and monitoring of the above tumors. Neurofibromas with accelerated growth, pain and hard texture. At the same time, systemic evaluation should be carried out, and patients with no signs of distant metastasis should undergo early surgical treatment as far as possible, and patients with distant metastasis can choose radiotherapy, chemotherapy and targeted therapy.

Neurofibromatosis type I (neurofibromatosis type 1, NF 1) is an autosomal dominant disorder with 50% of patients with familial and 50% sporadic mutations. NF 1 gene encodes neurofibromin, downregulates the activity of Ras-Raf pathway and suppresses cell proliferation; deficiency in neurofibrosis causes excessive activation of RAS pathway and causes uncontrolled cell proliferation in NF 1 patients^[5]. At present stage, surgery is the most commonly used, the main treatment, and neurofibroma has the characteristics of the nerve root growth, it is difficult to solve all lesions through surgery, lesions composed of extensive nerve and vascular tissue and normal tissue, surgical resection difficult and bleeding, incomplete resection after recurrence as high as 50%. NF 1 occurs in the head and neck. Some patients need secondary surgery 1 year after surgery, and the proportion of patients with partial resection after secondary surgery is higher than that of patients with subtotal resection.

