3.2.1 Main Indicators and Definitions

2-year progression-free survival rate (2-year PFS rate): the rate of no tumor progression or death from any cause within 2 years from postoperative treatment (whichever comes first).

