5.4 Definition of end of study (e. g. last subject completes last follow-up)

5.5 Statistical analysis

5.5.1 Sample size and basis for calculation

The estimated sample size was based on the objective response rate. The hypothesis of this study is that selmetinib sulphate can reduce the recurrence rate of patients after NF 1. The study parameters were set: $\alpha = 0.025$ (unilateral), Power=80%, and progression-free survival (PFS) in 20% of patients with NF 1 for 24 months. More than 50% of progression-free survival (PFS) in NF 1 patients. 17 cases were calculated using PASS 15.0 software, considering 10% shedding rate, 19 subjects should be included.

.5.52 Data analysis set (e. g. full analysis set, compliance protocol set, safety analysis set)

Statistical analysis will be performed using the SAS statistical software (V. 9.4, SAS Institute) Statistical analysis software for calculation, if no special instructions, the main indicators use one-sided test, control the first class error α is 0.025, the remaining indicators use two-sided test, one class error is $\alpha = 0.05$. To calculate confidence intervals, calculate two-sided 95% confidence intervals if not otherwise specified.

(1) Full analysis set (full analysis set, FAS): consisting of all subjects who received at least one drug / treatment and obtained efficacy assessment. This dataset was derived from all subjects after removing subjects in the least and reasonable way.

(2) Safety analysis set (safety analysis set, SS): a population treated at least once / once and having at least one safety evaluation data. In the safety analysis, all patients will be analyzed by the actual drug group.

(3) Compliance with the protocol set (per-protocol set, PPS): all concomitant medications that met the trial protocol and did not use the

impact effectiveness evaluation, good medication compliance (between 80% and 120%), excluded subjects who had major protocol violations and were judged to have a significant impact on the results. All protocol deviations causing the exclusion of subjects from the compliant protocol set will be described in detail in the Statistical Analysis Plan (SAP) and completed prior to data lock.

5.3 5 Statistical analysis plan

Data description of statistical analysis, analysis method of primary / secondary indicators / safety indicators, statistical school positive method, control of bias, stratification / subgroup / sensitivity analysis, etc

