Demographic, and other baseline characteristics

Based on the analysis of FAS set, the demographic data, medical history, vital signs and other baseline data were statistically described, where the measurement data (age, BMI, XX, etc.) gave mean, SD, minimum, maximum, median, and gave frequency and corresponding percentage for count data (gender, XXX, etc.).

Analysis of efficacy indicators

(1) Main efficacy indicators

Point estimates for the main evaluation index (PFS) and estimated two-sided 95% confidence intervals using the Clopper–Pearson exact probability method. If the lower limit of the 97.5% confidence interval is greater than the proportion of 24 months, the treatment group was considered better effective than the historical control.

We obtained the analysis model:

$$Y = b_0 + b_1 \cdot X_1 + b_2 \cdot X_2 + b_3 \cdot X_3 + \epsilon$$

In this equation, the X_i Represents the extent of tumor resection,

X_2 Represents the solid tumor size, X_3 Indicates the medication dose. b_0 Is the intercept, b_1 , b_2 , b_3 Is the regression coefficient of each factor, and the ϵ is the error term.

(2) Secondary efficacy indicators: analysis using FAS and PPS analysis sets. For survival measures, the digit survival time and its two-sided 95% confidence intervals were calculated. For the rate of each index, point estimates were performed and two-sided 95% confidence intervals were estimated using the Clopper-Pearson exact probability method. For the continuity index, the mean and two-sided 95% confidence intervals were calculated based on the normal distribution method, otherwise, the median and two-sided 95% confidence intervals were calculated based on the percentile method.

Safety index analysis

The SS set describes the incidence of adverse events / serious adverse events and adverse reactions, and lists the details of each adverse event in each subject, including the type and severity of adverse events. Safety and evaluation of laboratory indicators, vital signs, electrocardiogram and other safety related indicators, compare and evaluate the changes before and after treatment, and give statistical description of clinical evaluation (normal, abnormal without clinical significance, abnormal with clinical significance, not checked) before and after treatment.

Principles of handling of missing / deleted / lost to follow-up data

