Main index analysis adopts LOCF (last observation carried forward) method, that is, the main index data is not observed at the last time; the secondary indicators and safety indicators are not filled.

6. Research intervention*

6.1 Study intervention content (description of intervention content, implementation steps, dose and route of intervention drug, frequency of intervention, product of test group and control group, etc.)

All patients received oral selmetinib hydrosulphate capsules (20–50mg bid) daily for 30 days for 6 cycles, based on individualized patient body surface area (BSA).

6.2 Preparation / handling / storage / responsibilities (drug versus control article allocation plan when intervention should be specified)

The use of drugs must be recorded in the patient's medical record and in the corresponding location of the CRF. After the enrollment of the subjects and at the 1 and 2 months of follow-up, the executive nurse shall receive the corresponding number of drugs at the drug administrator, and the remaining drugs and boxes shall be returned to the drug administrator. If the drug is found or damaged during the preparation process, this box of drugs should not be used, the damaged drugs shall be treated as empty bottles, and other undamaged drugs shall be returned to the drug administrator together with the packaging box. The study center shall be responsible for the management of test drugs, including receiving, distribution, counting and recovery. The investigator shall ensure that the test drug is stored in a safe, independent and locked place at the study site and the storage conditions shall meet the storage requirements of the test drug. No one can be contacted without the consent of the investigator. Empty boxes shall be stored and managed as the test drug.

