6.4 Concomitant therapy (permitted adjuvant medication, complementary / replacement therapy)

If the subject has hypertension, diabetes, coronary heart disease and other diseases that need long-term drug control, the investigator and the relevant specialist should evaluate the impact of the disease and the relevant study protocol and determine the dose and duration of adjuvant medication.

6.4.1 Rescue (drug, treatment methods, relevant records.....)

The life hazards during the implementation of the clinical study protocol should be implemented in accordance with the clinical rescue plan, such as cardiopulmonary resuscitation, emergency airway management, emergency surgical treatment, relevant records during hospitalization should be recorded in the medical record system, after discharge should be recorded in the adverse event record form, and the investigator should analyze whether the rescue causes are related to the study and discuss and discuss synchronously in the rescue records.

7. Discontinuation of the study intervention / subject discontinuation and withdrawal*

7.1 Study Intervention discontinuation (reasons / criteria: such as how many adverse events occurred, length of study discontinuation, how data were collected during discontinuation and how to reactivate the study intervention, whether follow-up was continued during discontinuation)

If the Grade 5 adverse event of CTCAE 5.0 standard reaches 10% of the number of subjects, the study should be discontinued and the drug safety of the study protocol should be discussed to determine whether to adjust the dose of drugs in the study protocol, continue the follow-up during the study suspension, and maintain the follow-up record of the original

subject.

7.2 Subjects discontinuation / withdrawal from the study (possible reason for subject discontinuation; involving implantable device, discuss how to remove / replace, obtain alternative materials, later contact with the subject, etc.)

When the subject stops or withdraws from the study due to dissatisfaction with the treatment effect of the study plan or his own economic reasons, he should actively communicate with the subject, encourage the subject to actively treat and help them apply for public welfare funds to complete the treatment. If the subject clearly withdraws, the investigator can continue to complete the follow-up without the study intervention.

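### LOCF on the 24-month progression-free proportion counts early leavers as successes, and sections 4.3, 7.2 and 6.4/6.4.1 disagree on whether withdrawn subjects are still followed

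*Protocol*

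**What the plan says.** **Withdrawal and data.** Protocol section 4.3 deals with a subject who needs "the drug, treatment or surgery unrelated to the study". The investigator considers whether the need arose from a study adverse event, an accident or something else, and how it affects the course of the study. The only outcome then named is to "then advise the subject to receive conventional treatment after withdrawal and seal the subject data". Sealing is not defined.

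Section 7.2 opens with withdrawal for dissatisfaction with the treatment effect or for economic reasons, and closes more generally: "If the subject clearly withdraws, the investigator can continue to complete the follow-up without the study intervention". Section 6.4 provides for long-term concomitant medication, and section 6.4.1 lists emergency surgical treatment among rescue measures. Neither mentions withdrawal.

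**Endpoint and analysis.** Section 3.2.1 defines the primary measure as "the rate of no tumor progression or death from any cause within 2 years from postoperative treatment". Section 5.5 analyses it as a proportion with a Clopper–Pearson interval and declares success as follows: "If the lower limit of the 97.5% confidence interval is greater than the proportion of 24 months". The full analysis set is described as "consisting of all subjects who received at least one drug / treatment and obtained efficacy assessment". For missing primary data the rule is: "Main index analysis adopts LOCF (last observation carried forward) method". No exception is made for subjects withdrawn under section 4.3 or for any other reason.

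**The concern.** There are two linked problems.

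First, the protocol gives different answers to the question of what happens to a subject who stops. Section 4.3 points to withdrawal and sealed data, section 7.2 to optional continued follow-up, and sections 6.4 and 6.4.1 to other treatment with no withdrawal at all. In an open single-arm trial of 19 subjects, that leaves room to settle whether a subject is followed, dropped or imputed after the course of the disease is known.

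Second, LOCF is badly suited to this endpoint. Every subject starts progression-free, and that status can change only in one direction. For anyone who leaves before observed progression, the last observation is by construction favourable. Carrying it to 24 months turns an unknown outcome into a success, whatever the reason for leaving. With so few subjects and a threshold of 8, one or two such imputations are enough to break the stated error rate.

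**Working it through.** **Inputs (protocol section 5.5).** Null 24-month rate 20%, alternative 50%, one-sided α 0.025, power 80%, 17 cases, 10% shedding, 19 enrolled. The success rule names no number for its reference proportion; 20% is assumed here.

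**1. The plan's own figure.** Normal approximation with null and alternative variances:

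n = [(1.960·√(0.2·0.8) + 0.842·√(0.5·0.5)) / (0.5 − 0.2)]² = 16.13, so 17. Then 17/0.9 = 18.9, so 19. Both figures reproduce.

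**2. Success threshold with 19 analysed.** The Clopper–Pearson lower limit (two-sided 95%, that is 2.5% in the lower tail) is 0.163 for 7/19 and 0.2025 for 8/19. Success therefore needs at least 8.

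**3. Nobody carried forward.** P(X ≥ 8 | 19, 0.20) = 0.0233. P(X ≥ 8 | 19, 0.50) = 0.820.

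**4. d subjects carried forward as progression-free.** Assume that d of the 19 leave before any observed progression but have an efficacy assessment, so they stay in the full analysis set. The other 19 − d have a true rate of 20%. Success then needs only 8 − d among them:

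| d | Probability | Type I error |
|---|---|---|
| 0 | P(X ≥ 8 \| 19, 0.20) | 2.3% |
| 1 | P(X ≥ 7 \| 18, 0.20) | 5.1% |
| 2 | P(X ≥ 6 \| 17, 0.20) | 10.6% |
| 3 | P(X ≥ 5 \| 16, 0.20) | 20.2% |

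10% of 19 is 1.9, so d = 2 is about the plan's overall shedding.

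**5. The same effect expressed as a rate.** If a fraction w of would-be progressors is carried forward, the apparent null rate is 0.20 + 0.80w. For w = 5%, 10% and 20% this gives 24%, 28% and 36%, and P(X ≥ 8 | 19) is 6.3%, 13.4% and 36.9%. The values of w are assumptions.

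**6. If sealing means removal instead.** Suppose each would-be progressor is removed with probability 10% and the exact rule is applied to whoever remains. Type I error is then 2.4%, against 2.3% with nobody removed. Removal at this rate hardly changes the error.

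**7. Unknown status counted as failure.** With two of 19 unknown, at least 8 of the 17 observed must be progression-free. Type I error is P(X ≥ 8 | 17, 0.20) = 1.1%, and power is P(X ≥ 8 | 17, 0.50) = 68.5%.

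**The case against.** The strongest reply is that section 4.3 is limited to treatment unrelated to the study, so it does not on its face govern re-operation for the study tumour. That stands. The background in section 2.1 does say "Some patients need secondary surgery 1 year after surgery", and a reader might infer that section 4.3 turns failures of this kind into successes. The text does not show it. The boundary is not sharp, since section 4.3 also lists study adverse events as a possible cause, but that makes it unclear rather than proving the stronger reading.

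The conflict with section 7.2 is also softer than it first looks: 7.2 is introduced by other reasons for leaving, and it permits follow-up rather than requiring it. Even so, its closing sentence is general and does not fit with sealing the data.

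Nor does the protocol say in so many words that LOCF counts these subjects as progression-free. It follows from applying LOCF to this endpoint for anyone in the full analysis set. A sealed subject might instead be dropped, and the protocol does not settle which.

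Three further inferences fail:
- **Harm under-reported in the safety set.** Section 5.5 includes treated subjects with at least one safety evaluation, and section 8 requires all adverse events to be recorded. Nothing says that sealed data leave that set.
- **Removal favours the drug as LOCF does.** At 10% removal the type I error is 2.4%.
- **Section 4.3 causes a fall in power from 82.0% to 68.5%.** That is the exact test at 19 versus 17 subjects. The plan already expects 17 after shedding, having sized the trial by a normal approximation.

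Finally, how re-operation or new anti-tumour treatment enters the endpoint may be set out in the statistical analysis plan, which is not at hand. It is not shown to be an error here.

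**Conclusion.** The point holds in two parts. Sections 4.3, 7.2 and 6.4/6.4.1 are inconsistent on withdrawal and follow-up and must be reconciled. Separately, LOCF on the primary 24-month proportion is wrong as written: a single early leaver carried forward takes the type I error from 2.3% to 5.1%, twice the stated 2.5%, and two take it to 10.6%.

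The inflation belongs to LOCF after any early exit, not to section 4.3 in particular. Section 4.3 is one route to such an exit, and the protocol gives no rate for it; the 10% is overall shedding. The figures assume a reference proportion of 20%, 19 subjects analysed, and leavers who are in the full analysis set with no progression observed before they left.

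**What to change.** 1. In section 4.3, replace the sealing of data with retention of all data and follow-up for progression, survival and safety to 24 months, whatever other treatment is given. Align section 7.2 so that this follow-up is the rule rather than an option, subject to consent, and make both consistent with sections 6.4 and 6.4.1. No position is taken here on whether study treatment should stop.
2. In section 5.5, replace LOCF for the primary measure: count any treated subject with unknown 24-month status as not progression-free. Add a time-to-event estimate with censoring at the last assessment as a sensitivity analysis.
3. State, before data are seen, how re-operation or new anti-tumour treatment enters the endpoint, if the statistical analysis plan does not already do so.

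The cost is mainly wording, plus follow-up of subjects who would otherwise have been let go. The reported rate will be lower than under LOCF. Power is also lost for each unknown outcome: it is 68.5% by the exact rule if two of 19 are unknown and counted as failures, against 82.0% with all 19 known. Following withdrawn subjects under item 1 limits that loss.
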